15.6.6. Health Outcomes

HIVTSQs

Questionnaire (Questions 1-12 are scored 0-6)

CCI - This section contained Clinical Outcome Assessment data collection questionnaires or indices, which are protected by third party copyright laws and therefore have been excluded.

Total Treatment Satisfaction Score

- Total Treatment Satisfaction Score is computed with items 1-11. Items 1-11 are summed to produce a score with a possible range of 0 to 66.
- Item 12 will not be included in Total Treatment Satisfaction Score. Instead, it will be treated as a stand-alone item only.
- Higher scores represent greater treatment satisfaction as compared to the past few weeks.
- A maximum of 5 items can be missing, which can be imputed to reflect the mean of the completed item scores. If 6 or more items are missing, then the treatment satisfaction scale score should not be computed and instead be imputed using LOCF.

Individual Item Scores

- Items are rated as 6 [redacted] to 0 [redacted]
[redacted]
- Higher scores represent greater satisfaction with each aspect of treatment
 - For individual item scores outputs, missing scores will not be computed (according to Page 7 of the [HIVTSQ User Guidelines, 2016]) and instead be imputed using LOCF.

HIVTSQc

Questionnaire (Questions 1-12 are scored -3 to 3)

CCI - This section contained Clinical Outcome Assessment data collection questionnaires or indices, which are protected by third party copyright laws and therefore have been excluded.

CCI - This section contained Clinical Outcome Assessment data collection questionnaires or indices, which are protected by third party copyright laws and therefore have been excluded.

Total Treatment Satisfaction Score (change)

- Total Treatment Satisfaction Score is computed with items 1-11. Items 1-11 are summed to produce a score with a possible range of -33 to 33
- Item 12 will be computed as an individual item only.
- The higher the score, the greater the improvement in satisfaction with treatment; the lower the score, the greater the deterioration in satisfaction with treatment. A score of CCI [REDACTED]
[REDACTED]
- A maximum of 5 items can be missing, the missing scores will be imputed with the mean of the completed item scores. If 6 or more items are missing, then the overall treatment satisfaction scale score should not be computed and will remain missing.

Individual Treatment Satisfaction Change Item Scores

- Items are rated as +3 CCI [REDACTED]
[REDACTED] to -3 CCI [REDACTED]
- The higher the score, the greater the improvement in satisfaction with each aspect of treatment and the lower the score, the greater the deterioration in satisfaction with each aspect of treatment.

Questionnaire Version

- In main study, three versions of the HIVTSQc questionnaire are available with the questions the same and only the overhead text is different.
 - Q4W ATLAS to Q4W ATLAS-2M: for participants who randomized to Q4W arm in ATLAS and then randomized to Q4W arm in ATLAS-2M
 - Q4W ATLAS to Q8W ATLAS-2M: for participants who randomized to Q4W arm in ATLAS and then randomized to Q8W arm in ATLAS-2M
 - SOC to Q4W or Q8W ATLAS-2M: for participants who either were randomized to SOC arm in ATLAS or did not participate in ATLAS
- If a participant takes a wrong version of the questionnaire in main study, the data collected from the wrong version will be considered invalid and will not be included in the summary.
- In sub-study, all participants will take the same version of the questionnaire.

PIN

Questionnaire (Each question is scored 1-5)

CCI - This section contained Clinical Outcome Assessment data collection questionnaires or indices, which are protected by third party copyright laws and therefore have been excluded.

CCI - This section contained Clinical Outcome Assessment data collection questionnaires or indices, which are protected by third party copyright laws and therefore have been excluded.

Dimension Score (Chevat, 2008)

- Domains and Clusters
 - CCI [REDACTED]
 - CCI [REDACTED]
 - CCI [REDACTED]
 - CCI [REDACTED]
- 5 items not included in any of these domains and maintained as individual items (items CCI [REDACTED] [REDACTED])
- No overall score is calculated per the guidance
- The score of a domain is calculated as the mean of all items with the domain. Higher scores represent worse perception of injection.
- A maximum of <50% items can be missing within a domain, which can be imputed to reflect the mean of the completed item scores within the domain. Thus, if the number of missing items is ≥ 3 CCI [REDACTED], ≥ 2 CCI [REDACTED], ≥ 1 CCI [REDACTED], then the total score for the domain should not be computed and instead be imputed using LOCF (Section 15.7.2.2)

Individual Item Scores

- Items are rated on a 5-point scale, ranging from 1 (CCI [REDACTED], etc.) to 5 (CCI [REDACTED])

CCI [REDACTED] etc.).

- Lower scores represent worse perception of injection
- For individual item scores outputs, missing scores will not be computed and instead be imputed using LOCF (Section 15.7.2.2).

HAT-QoL (Holmes, 1999)

Questionnaire (Questions 1-14 are scored 1 to 5)

CCI - This section contained Clinical Outcome Assessment data collection questionnaires or indices, which are protected by third party copyright laws and therefore have been excluded.

Life satisfaction, HIV medications, disclosure worries

- The ratings for Items (a, b, c, d, e) will be recoded as below for analysis:

| Response option | Life Satisfaction | Medication/disclosure worries |
|-----------------|-------------------|-------------------------------|
|-----------------|-------------------|-------------------------------|
- A maximum of 50% question items can be missing within a domain, which can be computed and replaced with the mean of the completed item scores within the domain. Thus, if there are more than 1 item missing for Life Satisfaction, and more than 2 items missing for

Medication/disclosure worries, then the total score for the domain should not be computed and instead be imputed using LOCF (Section 15.7.2.2). A computed score for missing value will be added to calculate a total score for the domain. Total score for each of the three domains will be calculated and will be denoted as 'LISAT' for life satisfaction, 'MEDWO' for medication worries, and 'DISWO' for disclosure worries.

- Transform each dimension's total imputed value score to the 0-100 scale using the following formulae:

Life satisfaction: LISAT100=(100/(20-4))*(LISAT-4)

Medication worries: MEDWO100=(100/(25-5))*(MEDWO-5)

Disclosure worries: DISWO100=(100/(25-5))*(DISWO-5)

The higher the score, the greater satisfaction to life and the less worry. The transformed dimension score for each domain will be summarized and analysed.

Individual Item Scores

- For individual item scores outputs, missing scores will not be computed and instead be imputed using LOCF (Section 15.7.2.2).

ACCEPT (Acceptance/General Dimension) (Gilet, 2014)

Questionnaire (Questions 1-3 constitute to Acceptance/General Dimension)

CCI - This section contained Clinical Outcome Assessment data collection questionnaires or indices, which are protected by third party copyright laws and therefore have been excluded.

- Proportion of participants with individual item scores will be calculated.

Individual Item Scores

- Items are rated as 1 (CCI [REDACTED]) to 4 (CCI [REDACTED]) and '5' with (CCI [REDACTED]).
- Acceptance/General dimension score is calculated only if at least 2 items in the dimension are completed
- Items will be recoded to score as follows:

| Rating | Recode |
|--|--------|
| 1. Totally disagree/Not at all acceptable/ Not at all convinced: | 1 |
| 2. Somewhat disagree/Not very acceptable/ Not really convinced: | 1 |
| 3. Somewhat agree/ Somewhat acceptable/ Somewhat convinced: | 2 |
| 4. Totally agree/ Totally acceptable/ Totally convinced: | 3 |
| 5. I don't know: | 1 |

- The total score of the dimension is calculated as the mean of the recoded items of the dimension and then linearly transformed to be on a scale from 0 to 100: score, as below:

Total Score = (mean of the recoded items in the dimension - 1)/2 *100

- For individual item scores outputs, missing scores will not be computed and instead be imputed

| |
|--|
| using LOCF (Section 15.7.2.2). |
| Preference |
| Questionnaire |
| 
1. Based on your experience which HIV treatment do you prefer?
 
 Injectable Long-Acting HIV Treatment every 4 weeks
 
 Injectable Long-Acting HIV Treatment every 8 weeks (only select this answer if you received the 8-week injectable regimen of CAB LA + RPV LA during study)
 
 Oral daily HIV Treatment
 
 No preference
 |
| 
If you selected no preference, skip questions 2 and 3.
 
If you selected any other response, please continue and complete all questions.
 
2. What is the main practical attribute of this HIV therapy supporting your preference?
 
 Mode of administration
 
 Frequency of administration
 
 Time required for administration
 
 Scheduling visits
 
 Storing medications
 
 Impact of side effects
 
 Other, please specify
 
3. What is the main benefit related to this HIV therapy supporting your preference?
 
 More convenient, easier to integrate into one's daily life
 
 Less stressful
 
 Less stigma
 
 Easier to take the drug exactly as prescribed
 
 More efficacious
 
 Other, please specify
 |
| Questionnaire Version |
| 
 Two versions of questionnaire are available. The questions in each version of the questionnaire are the same and only the overhead text is different. 
 ATLAS (from Q4W ATLAS): for participants randomized to Q4W arm in ATLAS. ATLAS-2M (from SOC ATLAS or out): for participants who either were randomized to SOC arm in ATLAS or did not participate in ATLAS. |
| Data Handling |
| 
 Any missing values will remain missing (i.e. no imputation). |
| Reasons for Oral Bridging and Preference |
| Questionnaire |
| 
This questionnaire will be administered to participants receiving oral bridging during the Maintenance and/or Extension phase. It includes three questions regarding contact mode, main reasons for switch back to daily oral HIV medication and the HIV treatment preference. For the preference question, it asks participants to provide the statements supporting their preference. The details can be found in the eCRF.
 |
| Data Handling |

| |
|--|
| 
 Any missing values will remain missing (i.e. no imputation). |
| Preference Thigh Injection vs Gluteal Injection |
| Questionnaire |
| 
This questionnaire will be administered to sub-study participants. It includes two questions regarding injection site preference and contact mode. For the preference question, it asks participants to provide the statements supporting their preference. The details can be found in the eCRF.
 |
| Data Handling |
| 
 Any missing values will remain missing (i.e. no imputation). |
| Tolerability of Injection (NRS) |
| Questionnaire |
| 
 This questionnaire will be administered to sub-study participants. It includes two questions regarding the maximum level of pain experienced with the most recent injections and contact mode. The score for the maximum level of pain ranges from no pain (0) to extreme pain (10). |
| Data Handling |
| 
 Any missing values will remain missing (i.e. no imputation). |
| Reasons for Continuation/Switch |
| Questionnaires |
| 
 Reasons for Continuation questionnaire is collected for participants who were randomized to Q4W arm in ATLAS. Reason for Switch questionnaire is collected for participants who either were randomized to SOC arm in ATLAS or did not participate in ATLAS. |
| Data Handling |
| 
 If a participant takes a wrong questionnaire, for example, the participant randomized to SOC arm in ATLAS took Reasons for Continuation questionnaire, the data collected from this wrong version will be considered invalid and will not be included in the summary. If the questionnaire is taken beyond ± 2 weeks window from maintenance phase treatment start date (i.e. Study Day < -14 or Study Day > 14) will be considered not evaluable and will not be included in the summary. Any missing values will remain missing (i.e. no imputation). |

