12.5.1. Statistical Methodology Specification

| Statistical Analyses |
|--|
| Endpoints |
| 
 • Change from Baseline in 
 ○ HIVTSQs total treatment satisfaction score at Weeks 24,48 and 152 ○ ACCEPT general acceptance score at Weeks 24, 48 and 152 ○ HAT-QoL (Life satisfaction, HIV medications, disclosure worries) at Weeks 24 and 48 • Change from Week 8 in PIN Domain Scores (Bother of ISRs, Leg movement, Sleep, and Acceptance) and Individual Items Scores (Anxiety before, Pain, Satisfaction, Anxiety After, Willingness) at Weeks 24, 48 and 152 |

| Statistical Analyses | |
|---|--|
| Model Specification | |

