15.15.5.10. Health Outcomes Tables

| Health Outcomes Tables | | | | | | | |
|--------------------------------------|------------|------------|-------------------------|------------------------|---|---|-------------|
| No. in W48 | No. in W96 | No. in EOS | Population | IDSL / Example Shell | Title | Programming Notes | Deliverable |
| Perception of Injection (PIN) | | | | | | | |
| 6.1 | NA | NA | Intent-to-Treat Exposed | 201585/primary_02/T7.1 | Proportion of Subjects with Each Individual Item Score in PIN by Visit –LOCF (Maintenance Phase) | Display both arms. | W48 |
| 6.2 | NA | NA | Intent-to-Treat Exposed | 201585/primary_02/T7.2 | Summary of PIN in Domain Scores (Bother of ISRs, Leg movement, Sleep, and Acceptance) and Individual Items Scores (Anxiety before, Pain, Satisfaction, Anxiety After, Willingness) by Visit (Maintenance Phase) | Display both arms. | W48 |
| 6.3 | NA | NA | Intent-to-Treat Exposed | 201585/primary_02/T7.3 | Summary and Statistical Analysis of PIN in Domain Scores (Bother of ISRs, Leg movement, Sleep, and Acceptance) and Individual Items Scores (Anxiety before, Pain, Satisfaction, Anxiety After, Willingness) by Visit - LOCF (Maintenance Phase) | Display both arms. Adjust the first half of the footnote to “[1] Week 24/48 was compared with the 1st visit (Week 8) based on Wilcoxon signed-rank test, respectively.” | W48 |
| 6.4 | NA | NA | Intent-to-Treat Exposed | 201585/primary_02/T7.4 | Summary of PIN Change from Week 8 in Domain Scores (Bother of ISRs, Leg movement, Sleep, and Acceptance) and Individual Items Scores (Anxiety before, Pain, Satisfaction, Anxiety After, Willingness) by Visit (Maintenance Phase) | Display both arms. Adjust the footnote to “Note: Actual values are shown at Week 8.” | W48 |

CONFIDENTIAL

207966

| Health Outcomes Tables | | | | | | | |
|--|------------|------------|-------------------------|-------------------------|--|--|-------------|
| No. in W48 | No. in W96 | No. in EOS | Population | IDSL / Example Shell | Title | Programming Notes | Deliverable |
| 6.5 | NA | NA | Intent-to-Treat Exposed | 201585/primary_02/T7.5 | Summary of PIN Change from Week 8 in Domain Scores (Bother of ISRs, Leg movement, Sleep, and Acceptance) and Individual Items Scores (Anxiety before, Pain, Satisfaction, Anxiety After, Willingness) by Visit – LOCF (Maintenance Phase) | Display both arms. Adjust the footnote to “Note: Actual values are shown at Week 8.” | W48 |

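### The PIN scoring rules give opposite directions for domain scores and individual items with no visible recode, so one rule is wrong or the two kinds of score run opposite ways, unlabelled, in the same tables.

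*SAP*

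**What the plan says.** SAP section 15.6.6, PIN block, scores every question from 1 to 5. On domains it says: "The score of a domain is calculated as the mean of all items with the domain", followed directly by: "Higher scores represent worse perception of injection". It then sets some questions apart: "5 items not included in any of these domains and maintained as individual items". Under the sub-heading for individual item scores it repeats the five-point scale and says: "Lower scores represent worse perception of injection".

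Section 12.5.1 models both kinds of score in the same way: "Change from Week 8 in PIN Domain Scores (Bother of ISRs, Leg movement, Sleep, and Acceptance) and Individual Items Scores" at Weeks 24, 48 and 152. The model is an ANCOVA, reported as an adjusted Q8W minus Q4W difference with its 95% interval and p-value. Section 2.2 lists these changes as a secondary endpoint. Section 5.5.2 calls the PIN comparisons supportive, and section 12.5.1 applies no multiplicity adjustment to them.

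In sections 15.15.5.10 (Week 48) and 15.15.6.9 (Week 152), Tables 6.2 to 6.6 show domain scores and the five single items together. Table 6.1 is titled as "Proportion of Subjects with Each Individual Item Score in PIN by Visit". The programming notes for these tables do not say which direction is favourable.

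**The concern.** An average of unreversed items rises whenever any of its items rises, so it must run in the same direction as they do. The PIN block gives the average one direction and the items the other.

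What is at stake is interpretation. PIN results are reported as a signed difference between arms, and the sign means nothing until the direction is fixed. If the wrong sentence is carried into table footnotes or the study report, a difference in bother, pain or anxiety is described as favouring the arm it does not favour. The score names do not settle it: Acceptance, Satisfaction and Willingness sit beside Bother of ISRs and Pain, so a reader cannot safely guess the direction from the label.

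**Working it through.** No sample size, power or alpha figure is involved. The check is logical, followed by a count.

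**Direction of a mean.** With D = (x₁ + … + x_k)/k and no recoding, D increases in every xᵢ. If lower x is worse, lower D is worse. The two statements in section 15.6.6 therefore cannot both be true of the same items. Opposite directions would need a reversal, which on a 1 to 5 scale is x′ = 6 − x.

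**Is a reversal stated?** None is visible in the PIN block. In the same section HAT-QoL says its item ratings are recoded, and ACCEPT prints a recode table. HIVTSQs and HIVTSQc each give one direction for both total and items. PIN is the only instrument in the section where the two disagree.

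**Effect of a full reversal.** Change from Week 8 becomes (6 − x_t) − (6 − x₈) = −(x_t − x₈). Every change and every between-arm difference switches sign. The absolute difference, interval width and two-sided p-value stay the same.

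Illustration with assumed values, not taken from the SAP: mean changes of −0.5 (Q8W) and −0.3 (Q4W) give −0.5 − (−0.3) = −0.2. If higher is worse, this favours Q8W. If lower is worse, it favours Q4W.

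**Scope of the item rule.**

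| Reading | Consequence |
|---|---|
| All PIN items | The two rules conflict and at least one sentence is wrong as written |
| Only the five stand-alone items | No strict contradiction, but domain and item rows run opposite ways in Tables 6.2 to 6.6, unlabelled |

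Three things favour the first reading. The item block speaks of items on a five-point scale without restriction. The parallel HIVTSQs block uses the same sub-heading for items that do enter the total. Table 6.1 displays each item.

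**Count of between-arm comparisons** (section 12.5.1, three timepoints):
- domains: 4 × 3 = 12
- stand-alone items: 5 × 3 = 15

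One wrong sentence mislabels one of these sets.

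**The case against.** Four arguments deserve an answer.

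1. **Narrow scope.** The PIN block defines five items kept outside the domains, and sections 5.5.2 and 12.5.1 use nearly the same label for exactly those five. On that reading the argument from averaging does not apply, because these items enter no domain. This is a fair reading and cannot be excluded. It removes the strict contradiction, but it leaves mixed directions in shared tables.

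2. **Redaction.** The questionnaire, the domain item lists and the wording of the response anchors are blacked out. The anchors say what 1 and 5 mean, and a recode could sit in the hidden text. This stands to the extent that the absence of a recode is only an absence from the visible text, and that nobody can tell from this copy which sentence is right. It does not remove the conflict, because both direction sentences and the averaging rule are unredacted.

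3. **Low consequence.** The comparisons are supportive and outside the controlled testing sequence. This stands, and it limits how much weight the point carries.

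4. **Reach.** A reader might infer that all 12 + 15 = 27 comparisons are exposed to sign reversal, or that the analysis itself is wrong. The SAP does not support either. If one sentence is a slip, it misdescribes the domains or the stand-alone items, not both, and on the narrow reading possibly neither. No model, estimate, interval width or two-sided p-value changes under a full reversal.

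**Conclusion.** The point holds in limited form. Section 15.6.6 gives opposite directions for PIN domain scores and PIN items, and the visible rules contain nothing that reconciles them.

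- If the item rule covers all items, one statement is wrong. It reverses the reading of either 12 domain comparisons or 15 stand-alone item comparisons.
- If it covers only the five stand-alone items, the defect is one of labelling: opposite directions side by side without a warning.

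This rests on two assumptions: that no recode is specified in the blacked-out text, and that items within a domain share one direction. If some items within a domain ran the other way, an unreversed mean would also distort magnitude, but the visible text cannot show whether that applies.

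The primary endpoint, the key secondary virologic comparison and the HIVTSQs test are unaffected. Because a listed secondary endpoint is reported as a signed difference and the correction is small, it should be made.

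**What to change.** 1. Check the two direction sentences in section 15.6.6 against the instrument's response anchors and the scoring source already cited there, and correct the one that is wrong.
2. State whether the item rule applies to all PIN items or only to the five stand-alone ones.
3. Specify reverse coding (6 minus the score, before averaging) only if items within a domain have anchors that run the other way. For stand-alone items a stated direction is enough.
4. Add a direction footnote to PIN Tables 6.1 to 6.6 in the Week 152 deliverable, and to the Week 48 tables if they are reissued. PIN is not displayed in the Week 96, end-of-study or sub-study lists, so nothing is needed there.

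The cost is a wording change and table footnotes, plus a small programming change only if step 3 applies. The Week 152 PIN shells point to existing outputs from this study, so the Week 48 tables have probably been delivered already. Footnoting those would mean reissuing them.

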15.6.7. Virology

| |
|--|
| Genotype |
| Amino Acid Changes |
| 
 A mutation is considered present whenever the encoded amino acid residue differs from the amino acid that would have been encoded by the wild-type (e.g., HXB2, NL43) comparator gene; e.g., Q148K. If the encoded amino acid is seen as a mixture of wild-type and mutant amino acid, e.g., Q148Q/K, the mutated amino acid is considered present at the codon of interest. If the encoded amino acid is seen as a mixture of two or more amino acids, which may or may not include wild type, e.g., Q184K/H or Q184K/H/Q, etc., for the purposes of calculating the number of mutated amino acids, only one mutation is considered to be present at the codon of |

interest.

Representation of Amino Acid Changes

| Mutations | Amino acid change |
|-----------|---|
| T69S | Single mutation from amino acid 'T' (vendor reference) to 'S' (sample) at codon '69' |
| Q148H/K/R | Mixture of amino acid mutations 'H', 'K' and 'R' (sample) from amino acid 'Q' (vendor reference) at codon '148' |
| _69_1T | First insertion of amino acid 'T' (sample) at codon '69' |
| _69_2S | Second insertion of amino acid 'S' (sample) at codon '69' |
| _69_3S/A | Third insertion of a mixture of amino acids 'S' and 'A' (sample) at codon '69' |
| L74L/- | Mixture of amino acid 'L' (sample) and a deletion at codon '74' |
| V75- | Single deletion of amino acid (sample) at codon '75' |

Resistance Associated Mutations

- Known INI mutations associated with the development of resistance to CAB, BIC, RAL, EVG or DTG:

| | |
|---|---|
| Amino Acids in HIV Integrase for Analysis | H51Y, T66A/I/K, E92Q/V/G, Q95K, T97A, G118R, F121C/Y, E138A/K/T, G140A/C/R/S** , Y143C/H/R/K/S/G/A, P145S, Q146P, S147G, Q148H/K/R/N, V151A/L, S153F/Y, N155H/S/T, E157Q, G163R/K, S230R, R263K, L68V/I*, L74I/M*, E138D*, V151I*, G193E* |
|---|---|

NOTES:

- Draft listing; may be modified in case of additional substantive data availability.
- INI mutations listed taken from Stanford HIV Resistance Database (http://hivdb.stanford.edu/DR/cgi-bin/rules_scores_hivdb.cgi?class=INI cited 22Feb2021) and accessed on 28Mar2022.
- INI substitutions listed above in bold had a score of =60.

* Denotes additional INI mutations added as they were identified during in vitro passage of DTG or seen in a previous DTG study in INI-experienced participants (ING112574).

**G140R is potentially associated with CAB based on in-stream data monitoring of CVF participants.

- Major resistance mutations to other classes (i.e., NRTI, NNRTI, PI) as defined by the International Antiviral Society-USA (IAS-USA). The most up to date IAS-USA guidelines available at the time of DBL will be used in the analysis [[Wensing, 2019](#)].

| Class | Major Mutations |
|--------|---|
| NRTIs | M41L, A62V, K65R/E/N, D67N, 69 insert, K70E/R, L74V, V75I, F77L, Y115F, F116Y, Q151M, M184V/I, L210W, T215Y/F, K219Q/E |
| NNRTIs | L100I, K101E/P, K103N/S, V106A/M, V108I, E138/A/G/K/Q/R, V179L, Y181C/I/V, Y188C/L/H, G190S/A, H221Y, P225H, F227C, M230I/L |
| PIs | D30N, V32I, M46I/L, I47A/V, G48V, I50V/L, I54M/L/V, Q58E, T74P, L76V, V82A/T/F/L/S, N83D, I84V, N88S, L90M |

Note: List generated from IAS_USA Guideline, [[Wensing, 2019](#)]

- The pre-specified INSTI Mutations are identified as below:
 - Per the IAS-USA list of mutations associated with resistance to Bictegravir, Cabotegravir, Dolutegravir, Elvitegravir, or Raltegravir (IAS-USA 2019 resistance mutations update volume 27 issue 3, 2019): T66A/I/K, L74M, E92Q/G, T97A, G118R, F121Y, E138A/K/T, G140A/C/R/S, Y143C/H/R, S147G, Q148H/K/R, S153F/Y, N155H, R263K

- Observed mutations during in vitro passage of DTG or seen in a previous DTG study in INI-experienced subjects (study ING112574): H51Y, L74I, L68V/I, E92V, Q95K, E138D, Y143K/S/G/A, P145S, Q146P, V151I/L/A, N155S/T, E157Q, G163R/K, G193E, S230R
- Mutations per FDA request for Study 201584: Q146L, T124A
- The NNRTI resistance associated mutations (RAMs) are identified per IAS-USA NNRTI mutations (IAS-USA 2019 resistance mutations update volume 27 issue 3, 2019):
 - V90I, A98G, L100I, K101E/H/P, K103N/S, V106A/I/M/T, V108I, E138A/G/K/Q/R, V179D/F/L/T, Y181C/I/V, Y188C/H/L, G190A/E/S, H221Y, P225H, F227C/L/R, M230I/L, L234I
- The RPV RAMs are identified per IAS-USA NNRTI mutations (IAS-USA 2019 resistance mutations update volume 27 issue 3, 2019):
 - L100I, K101E/P, E138A/G/K/Q/R, V179L, Y181C/I/V, Y188L, H221Y, F227C, M230I/L

Phenotype

Phenotypic Susceptibility

Phenotypic susceptibility to all licensed antiretroviral drugs and CAB will be determined using PhenoSense HIV assays from Monogram Inc. and will be reported as fold change (FC) in IC50 relative to wild-type control virus NL4-3, i.e., FC of sample virus = IC50 of sample virus/IC50 of control virus.

Phenotypic susceptibilities will be categorised according to FC as shown in tables below (based on Monogram PhenoSense assay). Clinical cutoffs (where available) or biological cutoffs by PhenoSense will be used to define the phenotypic susceptibility of background treatment by Monogram.

Replication capacity is generated as part of standard phenotypic assays.

PhenoSense Algorithm

| Drug | Abbreviation | Class | PhenoSense cutoff |
|-----------------|--------------|-------|--------------------------|
| Abacavir | ABC | NRTI | (4.5 – 6.5) ^a |
| Lamivudine | 3TC | NRTI | 3.5 ^a |
| Didanosine | ddl | NRTI | (1.3 – 2.2) ^a |
| Stavudine | d4T | NRTI | 1.7 ^a |
| Zidovudine | AZT (ZDV) | NRTI | 1.9 |
| Emtricitabine | FTC | NRTI | 3.5 |
| Tenofovir | TDF (TAF) | NRTI | (1.4 – 4) ^a |
| Delavirdine | DLV | NNRTI | 6.2 |
| Efavirenz | EFV | NNRTI | 3 |
| Nevirapine | NVP | NNRTI | 4.5 |
| Etravirine | ETR | NNRTI | (2.9-10) ^a |
| Rilpivirine | RPV | NNRTI | 2.0 |
| Doravirine | DOR | NNRTI | 3 |
| Fosamprenavir/r | FPV/r | PI | (4-11) ^a |
| Atazanavir | ATV | PI | 2.2 ^a |
| Atazanavir/r | ATV/r | PI | 5.2 ^a |
| Indinavir/r | IDV/r | PI | 10 ^a |
| Lopinavir/r | LPV/r | PI | (9 – 55) ^a |
| Nelfinavir | NFV | PI | 3.6 |

| | | | |
|--------------|-------|-----|-------------------------|
| Saquinavir/r | SQV/r | PI | (2.3 – 12) ^a |
| Tipranavir/r | TPV/r | PI | (2 – 8) ^a |
| Darunavir/r | DRV/r | PI | (10 – 90) ^a |
| Ritonavir | RTV | PI | 2.5 |
| Enfuvirtide | T20 | FI | 6.48 |
| Cabotegravir | CAB | INI | 2.5 |
| Raltegravir | RAL | INI | 1.5 |
| Elvitegravir | EVG | INI | 2.5 |
| Dolutegravir | DTG | INI | (4-13) ^a |
| Bictegravir | BIC | INI | (2.5- 10) |

a. clinical cutoff (lower cutoff – higher cutoff).

Phenotypic Susceptibility

Phenotypic susceptibility to each drug in a participant's background regimen is determined by applying drug-associated cutoffs as defined by the PhenoSense algorithm to the phenotypic fold resistance as below:

Full Sensitivity

| Fold Change | Interpretation |
|--|----------------|
| > clinical lower cutoff or biological cutoff | resistant |
| ≤ clinical lower cutoff or biological cutoff | sensitive |

Partial Sensitivity

| Fold Change | Interpretation |
|--|---------------------|
| > clinical higher cutoff | resistant |
| ≤ clinical higher cutoff and > clinical lower cutoff | partially sensitive |
| ≤ clinical lower cutoff | sensitive |

PHENOTYP dataset from Monogram contains the phenotypic susceptibility for each drug derived from the cutoff listed above. Thus, phenotypic susceptibility (i.e. full sensitivity and partial sensitivity) will not be re-derived for our analysis.

Genotypic and Net Assessment Susceptibility

Genotypic and Net assessment susceptibility to all licensed antiretroviral drugs and CAB will be determined from Monogram Inc. Net assessment susceptibility will be reported with the categories of 'resistant', 'partially sensitive', and 'sensitive' as what will be performed for phenotypic susceptibility. Genotypic susceptibility will be reported with the categories of 'resistant', 'resistance possible' and 'sensitive'. Genotypic and Net assessment susceptibility will be assessed at time of CVF using plasma sample, Genotypic susceptibility may be assessed at baseline using PBMC.

